## 1.0 LIST OF ABBREVIATIONS

Abbreviation	Definition
AE	Adverse Event
CO	Carbon Monoxide
cpd	Cigarettes per day
CRF	Case report form
FTND	Fagerström Test for Nicotine Dependence
IRB	Institutional review board
M-M	Methadone-maintained
MINI	Mini International Neuropsychiatric Interview
NNS	Nicotine nasal spray
PNS	Placebo Nasal spray
PI	Principal Investigator
TLFB	Time-line follow-back
UDS	Urine drug screen
UCPC-OTP	UC Physicians Company, LLC Opioid Treatment Program

## 2.0 STUDY SCHEMA

**Figure 1: Study Schema**

### **3.0 STUDY SYNOPSIS**

**STUDY OBJECTIVES.** Smoking prevalence is over 83% in methadone-maintained (M-M) patients, these patients experience significant difficulty quitting, and there is evidence that a majority of M-M patients smoke most of their cigarettes in the 4 hours following methadone dosing. The objective is to provide a preliminary test of the ability of two pharmacological treatments, the nicotine nasal spray (NNS) and varenicline, relative to placebos, to reduce smoking during the four hours following methadone dosing.

**STUDY DESIGN.** This is a 7-week, randomized-controlled crossover study with a follow-up visit at week 8. Eligible participants will be randomized to receive the four interventions (NNS, varenicline, and placebos) in one of four orders to mitigate potential order effects.

**STUDY POPULATION.** 20 participants with elevated smoking following methadone dosing (i.e., smoking  $\geq 30\%$  of total daily cigarettes in the 4-hour post-dosing period), recruited from a large M-M program in Cincinnati Ohio, will be randomized into the study.

**TREATMENTS.** Nicotrol®NS (1 mg/dose, up to 40 doses/day), placebo for the Nicotrol®NS, varenicline tartrate (2 mg/day), and matching placebo for varenicline tartrate. Participants will be instructed not to smoke during medication evaluation weeks (weeks 1, 2, 4, and 7).

**ASSESSMENTS.** The primary outcome is the proportion of daily cigarettes smoked during the 4-hour post-methadone-dosing period as assessed by the Quitbit electronic cigarette lighter. Cigarettes per day is a key secondary outcome.

**PRIMARY ANALYSIS.** The primary outcome analysis will consist of two sets of statistical analyses, one comparing the effect of NNS to PNS on the proportion of daily cigarettes smoked during the 4-hour post-methadone-dosing period and one comparing the effect of varenicline to placebo on the proportion of daily cigarettes smoked during the 4-hour post-methadone-dosing period.

## **4.0 BACKGROUND AND RATIONALE**

Cigarette smoking, which accounts for 443,000 deaths annually in the United States, has an estimated prevalence of 83% in methadone-maintained (M-M) patients, a rate four times higher than the general population, and significantly higher than the rate observed in other outpatient substance use disorder treatment populations. M-M patients are interested in quitting smoking but experience significant difficulties with achieving smoking abstinence thus more intensive smoking-cessation interventions are likely required to help M-M patients to successfully quit smoking.

Insight into why smoking cessation is more difficult in M-M patients comes from studies evaluating the impact of opioid administration on smoking. Specifically, research has found that administration of methadone, buprenorphine, and heroin, all increase smoking. This observed increase may be due to the ability of cigarettes to increase the rewarding properties of opioids. For example, it has been demonstrated that participants work harder to receive a methadone dose when cigarettes are available concurrently than when methadone is offered alone. In addition, M-M patients report smoking around the time of their methadone dose to increase the pleasant effects of methadone. Based on the observed interactions between methadone and cigarette smoking, Elkader et al. suggest that smoking-cessation treatment may need to be customized for M-M smokers, for example, by ensuring adequate nicotine replacement therapy (NRT) be available during the 2-4 hours following methadone dosing. A study by Richter et al. also indicates that the 2-4 hours following methadone dosing is associated with greater levels of smoking, with greater rates of smoking observed in the 2 hours following dosing compared to the first 2 hours after waking, which is the period in which the highest rate of smoking occurs in non M-M smokers. Thus, in addition to the usual challenges faced by smokers trying to quit, M-M smokers may have an additional daily challenge following their methadone dosing. Identifying treatments that can ameliorate this challenge is of critical importance given the number of patients affected, with the number of these patients growing due to the opioid-use epidemic that has characterized recent years.

To our knowledge, no study has evaluated the ability of smoking-cessation interventions to ameliorate increased smoking following methadone dosing in M-M smokers and, thus, there is little empirical data upon which to select interventions or to base the design of a full-scale clinical trial. The present pilot study is designed to provide important information in this regard. For example, based on data from Richter et al, we anticipate that a majority of M-M patients (approximately 70%) will have their greatest level of smoking in the 2-4 hour post-methadone-dosing period but, to our knowledge, this finding has not yet been replicated. To be eligible for the present study, a M-M smoker must experience elevated levels of smoking in the 4 hours following methadone dosing, defined as smoking  $\geq 30\%$  of total daily cigarettes in that 4 hour time-frame. The process of screening patients for this study will provide valuable information about the relative frequency of patients who experience this level of elevated smoking during the post-methadone-dosing period. The present study will also provide preliminary information about the potential efficacy of two smoking-cessation interventions, the nicotine nasal spray (NNS) and varenicline, in reducing cigarette smoking during the four hours following methadone dosing in M-M patients.

The NNS was selected based on its ability to produce rapid peak levels of nicotine, which may approximate the rewarding effects obtained from smoking. In addition, the NNS will allow patients to individualize their dosing as needed, which might change as the effect of the methadone dose peaks. As the first study of NNS in M-M smokers, the present study will provide preliminary information about the utility of NNS in this population. One potential concern is that, in clinical trials, some patients have evidenced signs of dependence on the NNS as assessed by feelings of being dependent and by using the NNS in greater amounts or duration than recommended (package insert). The potential for developing dependence on NNS may be

## *Varenicline and nicotine nasal spray for M-M smokers – Version 4.6*

greater in M-M smokers in that they are, by definition, prone to addiction. In addition, M-M smokers have reported that methadone reduces the coughing and throat pain associated with smoking and it may be that methadone will have a similar effect in decreasing some of the potential unpleasant effects of the NNS (e.g., sinus/eye irritation, etc. ), which could serve to increase the overall pleasant effects of the NNS.

Varenicline was selected for the present study for several reasons. As a partial agonist for the  $\alpha 4\beta 2$  nicotinic acetylcholine receptor, varenicline should serve to decrease craving for cigarettes while also blocking their reinforcing effects and there is evidence that it is a more effective smoking-cessation treatment than bupropion. A pilot trial evaluating the safety and efficacy of varenicline, relative to placebo, for cocaine-using smokers in methadone-maintenance found a decrease in the number of cigarettes per day in the varenicline group despite cocaine use being the primary focus of the study. The present study will be the first to test the efficacy of varenicline in reducing smoking post-methadone-dosing.

## **5.0 STUDY OBJECTIVES**

### **5.1 Primary Objective**

1. To provide a preliminary test of the ability of two pharmacological treatments, the nicotine nasal spray (NNS) and varenicline, relative to placebos, to reduce cigarette smoking during the four hours following methadone dosing in M-M patients who experience elevated levels of smoking post-methadone-dosing.

### **5.2 Secondary Objectives**

1. To provide a preliminary evaluation of the ability of the NNS and varenicline, relative to placebos, to reduce total cigarettes per day in M-M patients
2. To assess the abuse liability of, and subjective feelings of dependence on, the NNS in M-M patients
3. To complete an initial evaluation of the comparative efficacy of the NNS and varenicline in reducing cigarette smoking during the 4-hours post-methadone dosing in M-M patients
4. To complete an initial evaluation of the comparative efficacy of the NNS and varenicline in reducing total daily smoking in M-M patients
5. To provide a preliminary evaluation of the ability of the NNS and varenicline, relative to placebos, to decrease opioid and nicotine withdrawal.
6. To provide a preliminary evaluation of the impact of the NNS and varenicline, relative to placebos, on the subjective experience of methadone.

## **6.0 STUDY DESIGN**

### **6.1 Overview of Study Design**

This is a 7-week, randomized-controlled crossover study with a follow-up visit at week 8. The portion of the study evaluating NNS and its placebo will be only single-blind, because of the inability to source an adequate matching placebo for the nicotine nasal spray. The portion of the study evaluating varenicline and

its matching placebo will be double-blind. Eligible participants will be randomized to receive the four interventions in one of four orders, with 5 patients assigned to each order; this design will serve to mitigate potential order effects. It should be noted that the study design is not fully counterbalanced in that varenicline and its placebo will always follow the NNS and its placebo. While it would be ideal to have a fully counterbalanced design, utilizing such a design would require an 11-week study, due to the dose escalation and washout periods required for varenicline/varenicline placebo. Given that the lack of a fully counterbalanced design impacts only the comparison of NNS and varenicline, which is a secondary objective/analysis, the decision was made to use the more efficient 7-week design.

## **6.2 Study Population**

Twenty participants, recruited from the UC Physicians Company, LLC Opioid Treatment Program (UCPC-OTP), a methadone-maintenance program in Cincinnati Ohio, will be randomized into the study. Participants will be recruited through printed and electronic advertisements at UCPC-OTP and through word-of-mouth from the UCPC-OTP staff.

## **6.3 Study Duration**

Enrollment is expected to take place over a period of approximately 6 months.

## **6.4 Participant Selection**

### **6.4.1 Inclusion Criteria**

Potential participants must:

1. be male or female, 18 years of age or older
2. be able to understand the study, and having understood, provide written informed consent in English
3. have been enrolled in the UCPC-OTP program for at least 30 days and be stable on the current methadone dose for at least 1 week
4. have smoked cigarettes for at least 3 months, have a measured exhaled CO level  $> 8$  ppm, and not planning to seek smoking-cessation treatment within the next 3 months
5. have a willingness to comply with all study procedures, including trying to stop smoking during designated weeks, and to comply with medication instructions
6. based on a week of Quitbit cigarette lighter assessments, with at least 5 days of useable data, smoke  $\geq 10$  cigarettes/day and smoke at least 30% of daily cigarettes within the 4-hour post-methadone-dosing period
7. if female and of child bearing potential, agree to use one of the following methods of birth control: oral contraceptives, contraceptive patch, barrier (diaphragm or condom), intrauterine contraceptive system, levonorgestrel implant, medroxyprogesterone acetate contraceptive injection, complete abstinence from sexual intercourse, hormonal vaginal contraceptive ring

## **6.4.2 Exclusion Criteria**

Potential participants must not:

1. have a current or past diagnosis of any psychotic disorder, or bipolar I or II disorder
2. have a psychiatric condition that, in the judgment of the study physician, would make study participation unsafe or which would make treatment compliance difficult
3. be a significant suicidal/homicidal risk
4. have a medical condition that, in the judgment of the study physician, would make study participation unsafe or which would make treatment compliance difficult. Such conditions include, but are not limited to:
  - liver function tests greater than 3X upper limit of normal
  - serum creatinine greater than 2 mg/dL
5. have had clinically significant cardiovascular or cerebrovascular disease within the past 6 months or have clinically significant ECG abnormalities
6. have taken an investigational drug within 30 days before consent
7. be taking concomitant medications that are contraindicated for use with the NNS or varenicline
8. be taking any concomitant medications that could increase the likelihood of smoking cessation (such as wellbutrin or nortriptyline)
9. have a known or suspected hypersensitivity to varenicline or the NNS
10. use/have used smoking-cessation programs with individual counseling or smoking-cessation medication treatments currently, or within 30 days before consent
11. have used electronic cigarettes or tobacco products, other than cigarettes, in the week before consent
12. be pregnant or breastfeeding
13. be anyone who, in the judgment of the investigator, would not be expected to complete the study protocol (e.g., due to relocation from the clinic area, probable incarceration, etc.)

## **6.5 Outcome Measures**

### **6.5.1 Primary Outcome Measure**

The primary outcome measure is the proportion of daily cigarettes smoked during the 4-hour post-methadone-dosing period as assessed by the Quitbit electronic cigarette lighter (manufactured by Quitbit, Inc.; Providence, RI). The Quitbit lighter records the time and date each time the lighter is activated, presumably to smoke a cigarette. The data from the lighter will be extracted at each weekly research visit.

The present trial will follow a procedure analogous to that utilized by Richter et al.; the Quitbit lighter will be used solely for tracking smoking, with the smoking-reduction component of the software disengaged. Study participants will be instructed on the proper use of the lighter, including only using the lighter to light a cigarette that they are going to smoke. They will also be provided with weekly log sheets to record any equipment problems or discrepancies between the smoking events recorded by Quitbit and the “actual” cigarettes smoked by the participant.

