### **6.5.2 Secondary Outcome Measures**

1. Cigarettes per day (CPD). The total number of cigarettes smoked each day will be assessed by the Quitbit lighter (see above). In addition, the Timeline Follow-back (TLFB) procedure will be used to assess the participants’ self-reported use of cigarettes, other tobacco products, alcohol and illicit substances for each day of the study. The CPD based on the TLFB will be used in statistical analyses in the event of Quitbit lighter problems for a given day.
2. Carbon monoxide (CO) level. CO in each participant’s breath will be tested using the Bedfont Micro+ Smokerlyzer® as outlined in Table 2. A CO level of  $\leq 8\text{ppm}$  will be used to verify reports of no smoking.
3. Nicotine withdrawal will be assessed with the Minnesota Nicotine Withdrawal Scale (MNWS), a self-assessment of the intensity (i.e., 0=none at all to 4=severe) with which the respondent is experiencing 8 nicotine withdrawal symptoms.
4. Opioid withdrawal will be assessed with the Subjective Opiate Withdrawal Scale (SOWS), a self-assessment of the intensity (i.e., 0=not at all to 4=extremely) with which the respondent is experiencing 16 opioid withdrawal symptoms.
5. Drug Effect Questionnaire (DEQ) - Subjective experience of methadone will be assessed with the 5-item DEQ, a PhenX Toolkit-recommended measure, in which participants rate the degree to which they experience 5 drug-related effects (i.e., feel a drug effect, high, like the drug, dislike the effect, would like more drug) by making a mark along a 100-mm line from 0 (not at all) to 100 (extremely).

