### **7.4 Active Treatment Phase**

As outlined in Figure 1, the active treatment phase is 7 weeks in duration. During this time, participants will receive all four medications and will be scheduled for one research visit per week. Participants will be instructed not to smoke during medication evaluation weeks, which are study weeks 1, 2, 4 and 7. During medication evaluation weeks (i.e., Weeks 1, 2, 4, and 7) the research visits will be scheduled to occur during day 6 or 7 of the week in order to maximize participant exposure to the medication/placebo prior to assessment. All assessments ideally will be completed after the participant has received his/her methadone dose and before the participant smokes a cigarette, with the exception of the baseline visit when participants will be allowed to smoke prior to completing the assessments.

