### **8.11 Treatment Plan**

Table 4 delineates the dosing schedule and the weeks during which medication efficacy will be evaluated. All participants will use NNS/PNS during days 1-7 of study weeks 1 and 2 and will be instructed to utilize the spray and to not smoke during those weeks. Participants will be taught how to deliver a 0.5 mg spray in each nostril and will be instructed that they may use the spray up to 40 times a day but no more than 5 times an hour. Participants will undergo dose escalation of varenicline/placebo during study weeks 3 and 6, and will be on full dose during weeks 4 and 7. Participants who are unable to tolerate the target dose (2 mg/day) will be titrated to the highest dose tolerated. Participants will be instructed to not smoke during weeks 4 and 7, which are the weeks during which the efficacy of varenicline/placebo will be assessed. It should be noted that participants assigned to a medication order in which varenicline is given before varenicline placebo (i.e., orders 1 and 3 in Table 1), will have a two-week washout period before placebo is tested - the first week is the official "wash out" week during week 5 and the second is week 6 during which the participant is undergoing dose escalation for placebo.

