### 9.2 Analysis Plan

All analyses will be completed using SAS, Version 9.3 (SAS Institute, 2010).

1. Primary outcome analysis. The primary outcome analysis will consist of two sets of statistical analyses, one comparing the effect of NNS to PNS on the proportion of daily cigarettes smoked during the 4-hour post-methadone-dosing period and one comparing the effect of varenicline to placebo on the proportion of daily cigarettes smoked during the 4-hour post-methadone-dosing period. The statistical approach taken to both sets of analyses will be the same. A normal mixed model regression will include treatment (active vs. placebo) and the proportion of cigarettes smoked during the post-methadone-dosing period during baseline as covariates. In addition, corrected Akaike Information Criterion (AICC), will be used to determine whether treatment order (see Table 1), time (days 1-7), and / or the treatment-by-time interaction should be included as covariates in the mixed model regression. The dependent variable will be the proportion of daily cigarettes smoked during the 4-hour post-methadone-dosing period from the weeks during which the medication/placebo is being evaluated (see Table 2). The baseline urine drug screen result (positive or negative for substances other than opioids) will be controlled for in the analyses.

2. Secondary outcome analyses. The present trial has six secondary objectives, the analytic approach taken for each is described below. The baseline urine drug screen result (positive or negative for substances other than opioids) will be controlled for in the analyses.

2a. Preliminary evaluation of the ability of the NNS and varenicline, relative to placebos, to reduce total cigarettes per day (CPD). This secondary outcome analysis will consist of two sets of statistical analyses, one comparing the effect of NNS to PNS on CPD and one comparing the effect of varenicline to placebo on CPD. The analytic approach utilized for the primary outcome analysis will be used for this analysis with the variable of interest being CPD (i.e., as opposed to the proportion of daily cigarettes smoked during the post-methadone-dosing period).

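### The primary share has no stated value on smoke-free days, which the plan asks participants to aim for, and no planned analysis measures how much is smoked in the 4-hour window

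*Combined protocol and SAP*

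**What the plan says.** Section 6.5.1 defines the outcome: "The primary outcome measure is the proportion of daily cigarettes smoked during the 4-hour post-methadone-dosing period", recorded by the electronic lighter. The denominator is not defined further.

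Section 9.2 takes the outcome from the evaluation weeks only: "The dependent variable will be the proportion of daily cigarettes smoked during the 4-hour post-methadone-dosing period from the weeks" in which active or placebo is assessed. The model is a normal mixed model, and AICC decides whether treatment order, "time (days 1-7), and / or the treatment-by-time interaction should be included as covariates in the mixed model regression".

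Those are the weeks in which participants are asked to stop. Section 7.4: "Participants will be instructed not to smoke during medication evaluation weeks, which are study weeks 1, 2, 4 and 7". Section 8.11 repeats this for the spray weeks and for varenicline: "Participants will be instructed to not smoke during weeks 4 and 7, which are the weeks during which the efficacy of varenicline/placebo" is assessed. Inclusion criterion 5 requires willingness to comply, "including trying to stop smoking during designated weeks".

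Section 6.5.2 allows for abstinence, since a CO level of 8 ppm or less "will be used to verify reports of no smoking". Its only substitution rule is: "The CPD based on the TLFB will be used in statistical analyses in the event of Quitbit lighter problems for a given day". That rule supplies a daily total, not a count inside the window.

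Sections 5.1 and 9.1 state the aim as reducing smoking in the four hours after the methadone dose. Cigarettes per day (CPD) is a key secondary outcome in the synopsis.

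**The concern.** There are two separate issues.

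**Smoke-free days.** A same-day share has no value when the day's total is zero. The plan asks for such days in exactly the weeks that supply the outcome, and it does not say whether they count as zero, are missing, or are absorbed into a weekly ratio. Software drops undefined values by default. The dropped days are the best possible responses, and if an active treatment produces more of them than its placebo, the loss differs by treatment. The choice could also be made after the data have been seen.

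**Amount against share.** The stated aim concerns how much is smoked in the window, whereas the outcome is how the day's smoking is divided. The two can part company, especially when participants are told to stop all smoking rather than only post-dose smoking. No planned analysis uses the window amount, so the stated objective has no direct answer.

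**Working it through.** **Inputs.** From section 9.3: N = 20, SD .27, within-subject correlation .80, two-sided alpha .05, difference .11, power 78%. From section 6.4.1: at least 10 cigarettes a day and a share of at least .30 at baseline. Abstinence rates, and a share of .40 on smoking days, are assumptions.

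**1. The plan's own figure.** SD of a paired difference = .27 × √(2 × (1 − .80)) = .171. Noncentrality = (.11/.171) × √20 = 2.88. A paired t-test on 19 df gives 78.0%, which reproduces the stated 78%.

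**2. Smoke-free days when treatment acts only through abstinence.** Let s be the share on smoking days and q the fraction of smoke-free days. Omitting those days estimates s(placebo) − s(active). Scoring them 0 estimates s(placebo)(1 − q(placebo)) − s(active)(1 − q(active)). With s = .40 under both treatments:

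| Smoke-free, placebo / active | Omitted | Scored 0 | Power for the scored difference, section 9.3 inputs |
|---|---|---|---|
| 5% / 10% | 0 | .40 × (.95 − .90) = .02 | 8% |
| 5% / 20% | 0 | .40 × (.95 − .80) = .06 | 32% |
| 10% / 37.5% | 0 | .40 × (.90 − .625) = .11 | 78% |
| 20% / 50% | 0 | .40 × (.80 − .50) = .12 | 85% |

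The third row was chosen to match the .11 of section 9.3. The zero in the second column follows from assuming no effect on smoking days. The power column holds SD and correlation fixed, although scoring zeros would change both. A simulation with an assumed between-person SD of .10 gave 8–9%, 31–44%, 69–89% and 71–94% for the four rows, and about 5% whenever the days were omitted. Those rates are illustrative, because that SD is not the plan's.

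In the same simulation, where abstinence varied between people, 1.3 of 20 participants on average (third row) and 2.8 (fourth row) had no usable day in at least one period. With the section 9.3 inputs, power for .11 is 73% with 18 pairs and 70% with 17.

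**3. The opposite case.** Suppose the share on smoking days really falls from .40 to .29 and 30% of days are smoke-free under both treatments. Omitting them keeps .11 (78% power). Scoring them 0 gives .70 × .40 − .70 × .29 = .28 − .203 = .077, and power falls to 48%.

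**4. Share against amount.** With w cigarettes in the window and o outside it, a common percentage fall f (below 100%) gives w(1 − f)/[(w + o)(1 − f)] = w/(w + o). So 6 + 14 cutting to 3 + 7 stays at .30.
- Equal absolute falls do move the share: 3/10 = .30 becomes 2/9 = .22.
- Window −50% with outside −70% raises it: 3/(3 + 4.2) = .42.
- An unchanged window with 80% more smoking outside lowers it: 6/(6 + 25.2) = .19.
- The .30 to .19 change used in section 9.3 needs a window fall of 45% if outside smoking is unchanged, 59% if outside falls 25%, and 73% if outside falls 50%.

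Now take 10 cigarettes a day with 4 in the window, averaging over people whose baseline share varies (assumed SD .10). Window/outside falls of 50%/40%, 50%/35% and 60%/30% move the share by −.041, −.058 and −.12. With the section 9.3 SD and correlation, power is about 17%, 30% and 85%. The simulation with SD .10 gave 39%, 68% and over 99%, again illustrative only. Window cigarettes and CPD rejected in about 100% of its runs in all three cases.

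**The case against.** **The share is the intended concept.** Section 4.0 defines elevated smoking as a share of the day's cigarettes, and eligibility, synopsis, analysis and power all use the share. Not responding to a proportional fall is what a share does. This stands: a reader might infer that the primary outcome is the wrong one, or is blind to any fall in window smoking. The documents support neither inference. The choice is consistent throughout, and the share does respond when window smoking falls by a larger percentage than other smoking. What remains is that sections 5.1 and 9.1 speak of reducing smoking and nothing planned measures that amount.

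**CPD covers it.** A flat share with a fall in CPD would point to a proportional fall, so the change would not be hidden. But CPD does not isolate the window.

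**Smoke-free days may be rare.** Participants smoke at least 10 a day, are not planning to seek cessation treatment, and come from a population that section 4.0 describes as having great difficulty quitting. This stands as to size: at 5%/10% the effect is small. A reader might infer that the primary test is bound to miss a real benefit; without any abstinence rate, the documents cannot support that.

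**A weekly pooled ratio would mostly avoid 0/0.** It would, except for a wholly smoke-free week. But the plan does not state one, and the day term points to daily values.

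**Scoring zeros is not neutral.** Correct, as step 3 shows. It argues for a stated rule with a sensitivity analysis, not for silence.

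**Conclusion.** The first point holds and should be settled before analysis. On the natural daily reading, the primary outcome is undefined on the days participants are asked to achieve, and following the plan would omit them. The harm is small if smoke-free days are rare (.02 at 5%/10%) and large if they are common and differ by treatment (.12 at 20%/50%). These sizes rest on assumed abstinence rates, a share of .40 and no effect on smoking days; a different pattern can reverse which rule has more power.

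The second point is exact arithmetic but weaker in consequence. It supports adding an analysis of the window amount. It does not show that the share is an invalid primary outcome or that the conclusion must move to another measure, so it is a recommendation and not a required correction.

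**What to change.** In sections 6.5.1 and 9.2:

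1. State that the denominator is that day's cigarettes. Score a day as zero window smoking when there are no lighter activations and the TLFB and log sheet confirm no smoking, supported by the weekly CO. Treat it as missing when they indicate lighter failure or use of another lighter. Report abstinent and missing days by treatment. Add a sensitivity analysis of the share that omits smoke-free days.
2. Pre-specify one supportive analysis of window cigarettes per evaluation day, zero on smoke-free days; for example, divided by the participant's baseline mean daily cigarettes, in the mixed model already planned. Interpret the share alongside it and CPD. The share may stay primary; if so, align the wording of sections 5.1 and 9.1 with it.

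**Cost.** Some wording, one supportive analysis and one sensitivity analysis. Lighter time stamps, log sheets, TLFB, CO and the baseline week are already collected. Scoring zeros mixes timing with abstinence and can lose power when smoke-free days are equally common under both treatments, hence the sensitivity analysis. The 78% in section 9.3 should not be quoted for the window amount, for which the documents give no SD, nor without qualification for the zero-scored share.
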